1.1 Synopsis

Protocol Title:

A Phase III Randomized, Modified Double-blind, Active-controlled, Multi-center Study to Describe the Immunogenicity and Safety of the Quadrivalent Recombinant Influenza Vaccine (RIV4) versus a Quadrivalent-inactivated influenza vaccine (IIV4) (Fluarix[®] quadrivalent) in Participants 18 Years of Age and Older in South Korea

Short Title:

Study Describing the Immunogenicity and Safety of Quadrivalent Recombinant Influenza Vaccine (RIV4) versus a licensed Quadrivalent-inactivated Influenza Vaccine (IIV4) (Fluarix[®] quadrivalent) in Participants 18 Years of Age and Older in South Korea.

Rationale:

VAP00016 study is being proposed to collect and analyze the immunogenicity and safety of the Quadrivalent Recombinant Influenza Vaccine (RIV4) versus a locally licensed quadrivalent-inactivated influenza vaccine (IIV4) (Fluarix[®] quadrivalent) that will serve as a control.

Clinical data generated with RIV4 support an indication in persons starting at 18 years of age and older. VAP00016 study will be conducted during the 2021-2022 Northern Hemisphere (NH) influenza season in 300 participants 18 years of age and older in South Korea.

Primary* Objectives	Primary Endpoints			
Immunogenicity				
 To describe the immune response induced by RIV4 and IIV4 in 18-49 and ≥ 50 years of age participants by hemagglutination inhibition (HAI) measurement method 	 HAI antibody (Ab) titers obtained on Day (D) 01 and D29 Individual HAI titers ratio D29/D01 Seroconversion: titer < 10 (1/dilution [1/dil]) at D01 and post-injection titer ≥ 40 (1/dil) at D29, or titer ≥ 10 (1/dil) at D01 and a ≥ 4-fold increase in titer (1/dil) at D29 Titer ≥ 40 (1/dil) at D01 and D29 Detectable titer ≥ 10 (1/dil) on D01 and D29 			
Safety †				
• To describe the safety profile of all participants in RIV4 and IIV4 groups	 Presence of any unsolicited systemic adverse event (AE) reported in the 30 minutes after vaccination Presence of solicited injection site, and systemic reactions occurring up to 7 days after 			

Objectives and Endpoints:

vaccination, (ie, pre-listed in the participant's diary and case report form [CRF])
Presence of unsolicited (spontaneously
reported) A Es up to 28 days after vaccination
Provide Ales up to 28 days after vaccination
• Presence of serious adverse events (SAEs),
including adverse events of special interest
(AESIs), throughout the trial period
Other endpoints recorded or derived as described
in the Gradient Law I are placed of derived as described
in the Statistical Analysis Plan (SAP). Depending
on the item, these could include nature (Medical
Dictionary for Regulatory Activities [MedDRA]
preferred term [PT]), time of onset, duration,
number of days of occurrence, grade of severity.
relationship to the vaccine action taken whether
the AE led to early termination from the study,
seriousness, or outcome.

*This study has no secondary or exploratory objectives

[†] Details on safety endpoints (terminology, definitions, and intensity scales) are presented in Table 10.1 and Table 10.2.

Type of design	Parallel, multi-center		
Phase	III		
Control method	Active-controlled		
	(control=IIV4)		
Study population	Participants 18 years of age and older		
	(2 age groups: participants 18-49 years of age and participants \geq 50 years of age)		
Country	South Korea		
Level and method of blinding	Modified double-blind		
Study intervention assignment method	Randomization		

Overall Design

Disclosure Statement:

This is a parallel-group prevention study with 2 arms that is participant and Investigator blinded.

A designated unblinded administrator at each study site knows which vaccine has been administered. The Investigator/sub-Investigator/staff involved in the sampling and safety assessment are blinded. The staff in charge of the immunogenicity assays is blinded.

Number of Participants:

A total of 300 participants are planned to be randomized.

Intervention Groups and Duration:

In each age group (18-49 years of age and \geq 50 years of age), eligible participants will be randomized in a 1:1 ratio to receive a single intramuscular (IM) injection of either RIV4 or IIV4 at D01.

The duration of each participant's participation will be approximately 6 months (180 days).

Data Monitoring Committee:

None.

For further details regarding the safety data collection, see Section 8 (Study Assessments and Procedures) and Section 10 (Supporting Documentation and Operational Considerations).

1.2 Schema

The graphical design of VAP00016 study is presented in Figure 1.1.

Figure 1.1 – Graphical study design

Abbreviations: BL, Blood sampling; V, Visit; PC, Phone call

1.3 Schedule of Activities (SoA)

Visit procedures are detailed in the Operating Guidelines.

Table 1.1: Schedule of activities

Phase III Study, 2 Visits and 2 Phone Calls, 1 Vaccination, 2 Blood Samples, 6 Months Duration Per Participant

Visit/Contact	Information to be collected in the CRF	Visit 1	Phone call 1	Visit 2‡	Phone call 2 (6 Months Follow-up)
Study timelines (days)		D01	D08	D29	D181
Time windows (days)		NA	[+2 D]	[+7 D]	[+14 D]
Visit procedures:					
Assent form/ Informed consent	X	Х			
Inclusion/exclusion criteria	X	Х			
Collection of demographic data	X	Х			
Collection of Medical history†	X				
	Significant Medical History	Х			
Urine pregnancy test (if applicable) §		Х			
Physical examination §§		Х		Х	
Pre-vaccination temperature		Х			
Randomization/allocation of participant number	X	Х			
Blood sampling (BL) [10 mL]	X	BL0001 Pre-vac		BL0002	
Vaccination (vac)	X	Х			
Immediate surveillance (30 min)	X	Х			
Diary card (DC) provided		Х			
Collection of solicited injection site and systemic reactions*	Х	Up to 7 days after vaccination (D01 to D08)			
Collection of unsolicited AEs	X	Up to 28 days after vaccination (D01 to D29)			
DC collected				Х	
Memory Aid (MA) provided				X	
MA checked					Х
Collection of concomitant medications	X	Х	Х	Х	Х

Visit/Contact	Information to be collected in the CRF	Visit 1	Phone call 1	Visit 2‡	Phone call 2 (6 Months Follow-up)
Study timelines (days)		D01	D08	D29	D181
Time windows (days)		NA	[+2 D]	[+7 D]	[+14 D]
Collection of SAEs, including AESIs	X	To be reported at any time during the study			
Collection of pregnancies	Х	To be reported at any time during the study			
Check participant status, remind participant to collect AEs and of planned next visit			Х		
End of active phase participation record ††	Х			Х	
End of 6-month safety follow-up participation record††	X				Х

Abbreviations: DC, diary card; mL, milliliter; NA, not applicable; Pre-vac, pre-vaccination; AE, adverse event; SAE, serious adverse event; AESI, adverse event of special interest; CRF, case report form; BL, blood sampling; MA, Memory Aid

† Including collection of the history of seasonal influenza vaccination.

- § Female participants of childbearing potential must have a negative urine pregnancy test prior to vaccination. Urine pregnancy test is applicable to childbearing potential female participant (to be considered of non-childbearing potential, a female must be post-menopausal for at least 1 year or surgically sterile).
- §§ Targeted physical examination based on medical history will be performed at Visit 1. Targeted physical examination may also be performed at Visit 2, as necessary.
- [‡] The Investigator or an authorized designee will interview the participants to collect the information recorded in the DC and will attempt to clarify anything incomplete or unclear.
- * Solicited injection site and systemic reactions will be collected from D01 to D08 by the participant using the DC provided. The DC is collected at D29.
- ^{††} Participants will be in the active phase from enrollment (D01) until completion of V02 (D29) and in the 6-Month safety follow-up from completion of V02 until approximately 6 months after V01.

2 Introduction

2.1 Study Rationale

VAP00016 study is being proposed to collect and analyze the immunogenicity and safety of the RIV4 versus a locally licensed IIV4 (Fluarix[®] quadrivalent) that will serve as a control arm.

RIV4 is a next-generation formulation that does not contain preservatives, antibiotics, egg protein, or latex, any of which may produce hypersensitivity reactions in some individuals. The rationale for and the advantages of the recombinant platform technology for the manufacturing of influenza vaccine have been well described in the medical literature (1-3). Clinical data generated with RIV4 support an indication for active immunization in persons 18 years of age and older for the prevention of influenza disease.

This Phase III, parallel, randomized, active-controlled, multi-centered, modified double-blinded, VAP00016 study will be conducted during the 2021-2022 Northern Hemisphere (NH) influenza season in 300 participants 18 years of age and older in South Korea.

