• To describe the safety profile of all participants in RIV4 and IIV4 groups	 Presence of any unsolicited systemic AE reported in the 30 minutes after vaccination Presence of solicited injection site, and systemic reactions occurring up to 7 days after vaccination, (ie, pre-listed in the participant's diary and CRF) Presence of unsolicited (spontaneously reported) AEs up to 28 days after vaccination Presence of SAEs, including AESIs, throughout the trial period Other endpoints recorded or derived as described in the SAP. Depending on the item, these could include: nature (MedDRA PT), time of onset, duration, number of days of occurrence, grade of severity, relationship to the vaccine, action taken, whether the AE led to early termination from the study, seriousness, or outcome.

*This study has no secondary or exploratory objectives

† Details on safety endpoints (terminology, definitions, and intensity scales) are presented in Table 10.1 and Table 10.2.

4 Study Design

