9.1 Statistical Hypotheses

No hypotheses will be tested. The analyses will be descriptive.

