9.4.3 Safety

Safety endpoints will be analyzed descriptively for participants in the safety analysis set (SafAS). The following safety parameters will be described by the 95% CI based on the Clopper-Pearson method in each age, intervention group and pooled age group. Additional parameters may be displayed as appropriate. The current MedDRA version will be used for the coding of all AEs/reactions.

Solicited Reactions

Number and percentage of participants with:

- Presence of solicited injection site reactions and systemic reactions occurring up to 7 days after injection
- Each solicited reaction according to time of onset, maximum intensity, and number of days of occurrence and action taken

Unsolicited Events and Reactions

Number and percentage of participants with:

- Any unsolicited immediate systemic event in the 30 minutes after injection according to System Organ Classes (SOC) and Preferred Terms (PT)
- Any unsolicited event and reaction 28 days after injection according to SOC and PT
- Any unsolicited event/reaction according to time of onset, maximum intensity, and duration

SAEs

Number and percentage of participants with:

• Any SAE within 28 days after injection and throughout the entire study according to SOC and PT, seriousness and outcome

AESIs

- Number and percentage of participants with:
- Any AESI within 28 days after injection and throughout the entire study according to SOC and PT, seriousness and outcome

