3.4.2.1 Immunogenicity

The analysis of Hemagglutinin inhibition (HAI) Ab response measured at D01 and D29 will be performed by age subgroup, intervention group and pooled age group, including but will not be limited to:

- Geometric mean of HAI Ab titer (GMT) and 95% CI at D01 and D29
- Geometric mean fold-rise (GMFR) of HAI Ab titer and its 95%CI. Fold-rise is computed as individual titer ratio of post-vaccination value divided by baseline value.
- Number and percentage of participants with seroconversion (seroconversion rate): titer < 10 (1/dilution [1/dil]) at D01 and post-injection titer ≥ 40 (1/dil) at D29, or titer ≥ 10 (1/dil) at D01 and a ≥ 4-fold increase in titer (1/dil) at D29
- Number and percentage of participants with titer ≥ 40 (1/dil) at D01 and D29
- Number and percentage of participants with detectable titer ≥ 10 (1/dil) at D01 and D29

The 95% CIs for the GMTs and GMFR will be calculated using a normal approximation of log_{10} -transformed titers. The 95% CIs for the proportions will be based on the Clopper-Pearson method (1).

The ratios of GMTs (RIV4/IIV4) in each age group and pooled age group will be obtained between groups with the 95% CIs calculated using a normal approximation of log₁₀-transformed titers. The differences in the seroconversion rates between groups in each age group and pooled age group will be computed along with the 2-sided 95% CIs by the Wilson-Score method without continuity correction (2).

Reverse cumulative distribution curves in each age group and pooled age group against each strain will be performed for baseline (D01) and post-vaccination immunogenicity (D29).

The primary immunogenicity analyses will be performed on the Per-Protocol Analysis Set (PPAS) and on the Full Analysis Set (FAS). Details of both analyses sets are described in Section 3.3.

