3.4.2.2 Safety

The following safety data will be summarized using Clopper-Pearson method to estimate the 95% CI by age subgroup, intervention group and pooled age subgroups. The current Medical Dictionary for Regulatory Activities (MedDRA) version will be used for the coding of all AEs/reactions.

Solicited Reactions

Number and percentage of participants with:

- Presence of solicited injection site reactions and solicited systemic reactions occurring up to 7 days after injection
- Each solicited reaction according to time of onset, maximum intensity, and number of days of occurrence and action taken

Unsolicited Events and Reactions

Number and percentage of participants with:

- Any unsolicited immediate systemic event in the 30 minutes after injection according to System Organ Classes (SOC) and Preferred Terms (PT)
- Any unsolicited event and reaction 28 days after injection according to SOC and PT
- Any unsolicited event/reaction according to time of onset, maximum intensity, and duration

SAEs

Number and percentage of participants with:

• Any SAE within 28 days after injection and throughout the entire study according to SOC and PT, seriousness, and outcome

AESIs

Number and percentage of participants with:

• Any AESI within 28 days after injection and throughout the entire study according to SOC and PT, seriousness, and outcome

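### Between-vaccine estimates with 95% CIs are pre-specified for immunogenicity but not for safety; a short list of RIV4 minus IIV4 safety differences would be a cheap improvement

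*Protocol*

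**What the plan says.** Protocol 2.1 gives the purpose of the study: "VAP00016 study is being proposed to collect and analyze the immunogenicity and safety of the RIV4 versus a locally licensed IIV4". The safety objective in protocol Section 3, Table 3.1 is "To describe the safety profile of all participants in RIV4 and IIV4 groups". It is primary, as is the immunogenicity objective. Protocol 9.1 makes the whole study descriptive: "No hypotheses will be tested. The analyses will be descriptive".

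For safety, protocol 9.4.3 says that the endpoints will be "described by the 95% CI based on the Clopper-Pearson method in each age, intervention group and pooled age group". It adds an open clause: "Additional parameters may be displayed as appropriate". SAP 3.4.2.2 matches the protocol on method ("The following safety data will be summarized using Clopper-Pearson method to estimate the 95% CI by age subgroup, intervention group and pooled age subgroups") but does not repeat the open clause. SAP Table 3.1 lists numbers and percentages of participants with 95% CIs, and event counts for unsolicited AEs. None of these places names a difference or ratio between vaccines for any safety endpoint.

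Immunogenicity is treated differently. Protocol 9.4.2 and SAP 3.4.2.1 specify RIV4/IIV4 ratios of GMTs with 95% CIs. On seroconversion, SAP 3.4.2.1 states: "The differences in the seroconversion rates between groups in each age group and pooled age group will be computed", with a two-sided 95% CI by the Wilson-score method without continuity correction. The sample size sections (protocol 9.2, SAP 3.2) already quote a precision for differences between proportions.

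**The concern.** Both primary objectives are descriptive and both rest on the same randomised comparison, yet only one gets a between-vaccine estimate with its uncertainty. Being descriptive does not explain this, because a difference with a CI is an estimate and not a test, and the plan already takes that view for immunogenicity.

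The contrast is of interest here. Protocol Table 6.1 lists 45 µg of HA per strain for RIV4 and 15 µg for IIV4, and protocol 2.2 makes a comparative statement about antigen amount and adverse reactions. The control arm is the trial's direct source of information on that contrast.

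With per-arm intervals only, a reader may take overlapping intervals as a sign of similar safety. Overlap of two 95% intervals is not a 95% statement about the difference. A difference can be missed whichever vaccine is the more reactogenic. If differences are instead added after the data are seen, the choice of endpoints is no longer pre-specified.

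**Working it through.** **Inputs.** From protocol 9.2 and SAP 3.2: 75 participants per age-by-vaccine cell, so 75 × 2 = 150 per vaccine with ages pooled; 5% drop-out, giving 75 × 0.95 = 71.25, taken as 71 evaluable. Interval methods are those the plan names: Clopper-Pearson for one proportion, Wilson score without continuity correction for a difference. The documents give no reactogenicity rates, so every rate below is an assumption.

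**The plan's own figures first (71 per group, 50%).**
- Clopper-Pearson: the lower limit is the 2.5% quantile of Beta(x, n−x+1) and the upper limit the 97.5% quantile of Beta(x+1, n−x). With n = 71 and x = 35.5 the width is 24.2 points. The plan states 24.2%.
- Wilson limits at 50% are 38.67% and 61.33%, a half-width of 11.33. The difference CI width is 2 × √(11.33² + 11.33²) = 32.0 points. The plan states 32.0%.

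Both figures reproduce. They also show the gap: two intervals 24.2 points wide separate only when the percentages differ by about 24 points (12.1 + 12.1), while the difference CI excludes zero at about 32.0 / 2 = 16 points.

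**Smallest observed excess that shows up.**

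| Per arm | Lower arm | Per-arm intervals separate | Difference CI excludes 0 |
|---|---|---|---|
| 75 | 30/75 (40%) | 48/75, 24.0 points | 42/75, 16.0 points |
| 150 | 45/150 (30%) | 70/150, 16.7 points | 62/150, 11.3 points |

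**Worked example.** Take 45/150 (30.0%, Clopper-Pearson 22.8 to 38.0) in one arm and 26/150 (17.3%, 11.6 to 24.4) in the other. The intervals overlap. The difference is 12.67 points. The Wilson limits are 23.24 to 37.76 and 12.11 to 24.19.
- Lower limit: 12.67 − √((30.00 − 23.24)² + (24.19 − 17.33)²) = 3.0.
- Upper limit: 12.67 + √((37.76 − 30.00)² + (17.33 − 12.11)²) = 22.0.

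The 95% CI of 3.0 to 22.0 excludes zero.

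**How often, by exact enumeration of both binomial distributions.**

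| Assumed rates | Per arm | Intervals separate | Difference CI excludes 0 |
|---|---|---|---|
| 40% vs 25% | 150 | 46% | 80% |
| 40% vs 25% | 75 | 17% | 50% |
| 30% vs 50% | 75 | 34% | 73% |
| 10% vs 25% | 75 | 30% | 68% |
| 30% vs 30% | 150 | 0.4% | 5.0% |

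With equal rates anywhere from 10% to 50%, the intervals separate in 0.26% to 0.46% of trials at 75 or 150 per arm. The difference CI excludes zero in 4.5% to 6.0%.

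**How long the list should be.**
- Protocol Tables 10.1 and 10.2 list 6 injection-site and 8 systemic reactions. Each at any grade and at Grade 3 gives 14 × 2 = 28. Any injection-site, any systemic, unsolicited AE, unsolicited AR and SAE bring this to 33, and 33 × 3 (two age groups plus pooled) = 99 intervals.
- A titer ≥ 40 difference at D29 would add 4 strains × 3 age sets × 2 analysis sets = 24.
- Five headline endpoints give 5 × 3 = 15. At a nominal 5% each, about 15 × 0.05 = 0.75 would exclude zero by chance on average, against about 99 × 0.05 = 5 for the long list.
- For SAEs a difference adds little: 0/150 versus 0/150 gives −2.5 to +2.5 points.

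**The case against.** The strongest reply is that the study does what it set out to do. The objective is to describe, no hypothesis is tested, and per-arm percentages with exact CIs meet that objective. That stands: the plan contains no contradiction or wrong figure on this point.

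Second, no passage says that arms will be compared by overlap of intervals. The percentages show the point difference, and anyone can compute a Wilson-score interval from the published counts. This also stands. The operating figures above describe how a reader might use the output, not a rule in the plan.

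Third, protocol 9.4.3 permits additional parameters, and the immunogenicity list is not exhaustive. These clauses allow a between-arm difference but do not commit to one, and SAP 3.4.2.2 does not carry the clause over. They soften the point without removing it.

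Fourth, more intervals without multiplicity control invite chance findings. That is fair against a long list of around 99, and it is the reason to keep the list short.

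Two stronger readings are tempting. A reader might infer that the active control is there to demonstrate a safety difference or equivalence; the title, objectives and Section 9.1 do not support that. A reader might also infer that the omission favours RIV4. The documents give no reactogenicity rates, and overlap would hide an RIV4 advantage as readily as a disadvantage.

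**Conclusion.** The point holds as a modest gap in pre-specification that is cheap to close. Both documents give the randomised RIV4 versus IIV4 contrast an estimate and a 95% CI for immunogenicity, and neither does so for safety.

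The consequence depends on the reader. Someone who judges by interval overlap needs an observed excess of about 24 rather than 16 points within an age group, or about 17 rather than 11 with ages pooled. At the assumed rates tabulated for 75 per arm, that reader would notice a true difference half as often, or less, than with the difference CI. These sizes rest on the assumed rates and on full enrolment of 75 per cell. The pattern was the same across assumed rates of 10% to 65%.

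**What to change.** In SAP 3.4.2.2 and protocol 9.4.3, pre-specify the RIV4 minus IIV4 difference in percentages, with the two-sided 95% Wilson-score CI without continuity correction, by age group and pooled, for:
- any solicited injection-site reaction;
- any solicited systemic reaction;
- any Grade 3 solicited reaction;
- any unsolicited AE within 28 days;
- any unsolicited AR within 28 days.

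Label these roughly 15 intervals descriptive and unadjusted for multiplicity. Individual solicited reactions, SAEs, AESIs and the SOC/PT tables stay per arm. Optionally, add the difference in titer ≥ 40 at D29 per strain, which also has no specified between-vaccine estimate.

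The cost is wording in two sections and an extra column in a few tables, using a method already planned for seroconversion. The downside is a few more descriptive intervals without multiplicity control. No new data, participants or methods are needed.

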2.2 Background

Influenza is a highly contagious, acute viral respiratory disease caused by infection with influenza viruses (4). Influenza causes recurrent epidemics of acute disease in persons of all ages and is currently estimated to account for 290 000 to 650 000 excess deaths annually worldwide, most of which occur in older adults (5).

The incubation period of influenza ranges from 1 to 4 days and peak virus shedding usually occurs from 1 day before the onset of symptoms to 3 days after. Typical features of influenza include abrupt onset of fever and respiratory symptoms such as cough (usually nonproductive), sore throat, and coryza, as well as systemic symptoms such as headache, muscle aches, and fatigue. Complications of influenza include primary viral pneumonia, secondary bacterial pneumonia, and exacerbation of underlying medical conditions such as chronic obstructive pulmonary disease and cardiovascular diseases (4).

Annual influenza vaccination is the best means for preventing influenza illness and its complications. It has been shown to be effective in reducing influenza-associated morbidity and mortality. Health care providers should recommend vaccination for all persons ≥ 6 months of age who do not have contraindications to vaccination (6).

Influenza control depends upon epidemiological data of influenza virus circulation to ensure that vaccination is timed ahead of peak transmission. For most countries, the World Health Organization (WHO) recommended timing of vaccination was appropriate for (ie, within 4 months before) the timing of the influenza peak activity (7).

Each year, WHO convenes technical consultations in February and September to recommend viruses for inclusion in influenza vaccines for the NH and the Southern Hemisphere (SH) influenza seasons, respectively. Generally, countries in East Asia experienced increased influenza activity from December 2019, with influenza A(H3N2) predominant in China and Mongolia and A(H1N1)pdm09 viruses predominant in Japan and South Korea (8).

Influenza comprises not only a burden on the medical system but also has a huge socioeconomic burden in Korea. The national influenza surveillance system has played an important role in identifying influenza epidemic patterns and virus characteristics in Korea (9).

The current surveillance system operated by the Korea Centers for Disease Control & Prevention (KCDC) provides an understanding of the characteristics of serious influenza and its disease burden. The hospitalization and mortality surveillance system are being operated, but the data collected are limited and cannot be used to fully understand the clinical course (9).

Nevertheless, it's known that in South Korea, approximately 7 000 patients are hospitalized and 400 000 are treated as outpatients annually for seasonal influenza (10).

According to data from 2003 through 2013 (10-year period), the overall all-cause excess annual mortality rate per 100 000 people was 5.97, whereas it was 46.98 for adults \geq 65 years of age. In this same period, a total of 2 570 939 deaths were reported with an average crude mortality rate of around 10 deaths per 100 000 people each week, and a slightly higher mortality rate during the winter. During this period, South Korea experienced 2 influenza epidemics in most years, with the first peak in the early winter (December through January) followed by a smaller peak in the late spring (April through May) (11).

To reduce the disease burden of influenza, the South Korean government has recommended influenza vaccination for the target groups, including children under 18, people 50 years of age and above, pregnant women, and those with chronic diseases (12).

Since 2005, free trivalent influenza vaccine (TIV) has been provided in South Korea for the elderly above 65 years of age by the National Immunization Program (NIP). Despite the successful implementation of the influenza NIP, more than 2 900 deaths occur annually due to influenza, most of them in the elderly (11).

Since 2000, 2 strains of influenza B have circulated concurrently. There are 2 lineages of the influenza B virus, namely, Victoria, and Yamagata. However, only 1 lineage is included in the TIV as recommended by the WHO. As both lineages circulate simultaneously, vaccine mismatch is the foremost problem. In South Korea, the degree of influenza B mismatch was estimated to be 41.7% based on analysis during 4 influenza seasons (2007-2008, 2009-2010, 2011-2012, and 2013-2014). To overcome this problem, a quadrivalent influenza vaccine (QIV) was developed, and since 2014, people can receive either TIV or QIV (12).

KCDC recommends annual vaccinations for those at high risk. As part of the NIP, seasonal influenza vaccines are reimbursed each year during the flu season for adults \geq 65 years of age, and more recently (for the 2017-2018 flu season) for children between 6 and 59 months of age (13).

The estimated all-cause mortality rate associated with any influenza virus infection was highest in the elderly (≥ 65 years of age) and middle-aged adults 45-64 years of age, with an average of 46.98 and 2.73 excess deaths per 100 000 people, respectively (11).

Deaths caused by 7 major causes, including respiratory, cardiovascular, cancer, diabetes mellitus, renal, chronic liver, and degenerative nervous system diseases, accounted for almost 70% of the all-cause excess mortality attributable to influenza (11).

Background of the Study Intervention

RIV4 is a recombinant hemagglutinin (rHA) influenza vaccine indicated for active immunization against disease caused by influenza A subtype viruses and type B viruses consisting of 4 full-length rHA derived from the 4 influenza strains (2 A subtypes and 2 B lineages) selected by the WHO. These proteins are produced in a continuous insect cell line *expres*SF+[®], derived from Sf9 cells of the fall armyworm *Spodoptera frugiperda*, and grown in a serum-free medium composed of chemically defined lipids, vitamins, amino acids, and mineral salts. Each of the 4 hemagglutinins (HAs) is expressed in this cell line using a baculovirus vector (*Autographa californica* nuclear polyhedrosis virus [AcNPV]) (14).

The HA genes are cloned independently into a baculovirus expression vector plasmid. After confirmation of the correct sequence, the deoxyribonucleic acid (DNA) sequences are inserted into AcNPV by homologous recombination. Recombinant viruses containing the respective HA genes are then used to express the HAs in the high-yielding insect *expres*SF+ cell line under serum-free conditions. Use of recombinant DNA techniques to produce vaccine antigen expressed in cell culture is a method that avoids growing the influenza viruses in embryonated hen's eggs or any cell line, thus avoiding genetic mutations that may reduce the efficacy of the vaccine. The recombinant proteins are highly purified, and the vaccine contains no egg protein, preservatives or antibiotics, any of which may produce hypersensitivity reactions in some individuals (14).

RIV4 is a sterile liquid preparation for IM injection in a single-dose pre-filled syringe. RIV4 contains 45 μ g of rHA antigen per virus strain per 0.5 mL dose (total recombinant HA of 180 μ g). The high purity of a recombinant antigen enables the administration of a higher concentration of rHA antigen without an increase in adverse reactions (ARs) (14).

